MBDC-The Mindfulness Based Dementia-Care Study-Protocol

NCT Number: NCT04062227

PI: [name], PhD

Version 5

Original Date: Aug 16, 2019

Summary

Mindfulness refers to a particular type of attention that is focused on the present moment, with non-judgmental awareness and acceptance of that experience, with a general attitude of openness and curiosity. Mindfulness-Based training was designed to enhance the range and use of coping skills, decrease levels of stress, improve mood, and reduce tendencies to react in maladaptive ways ¹⁻³. We are evaluating a program being conducted at multiple sites, called the Mindfulness Based Dementia-Care (MBDC) in caregivers (CG) for dementia, which combines the traditional mindfulness training approaches with dementia specific education. MBDC is housed by The Presence Care Project non-profit, which offers training to certify MDBC Facilitators. The overall objective of this study is to evaluate the efficacy of the Mindfulness-Based Dementia Care Program by conducting a prospective, pre-post, observational study with members participating in the MBDC program across multiple sites. Results will be included in a future grant submission for a larger scale research project that will include a control group, as well as objective measures, such as cortisol levels, and blood pressure.

Study aims

Aim 1: Evaluate change in self-reported measures in caregivers participating in Mindfulness Based Dementia-Care (MBDC) program.

Primary Outcome: Change in pre-post stress scores.

Secondary Outcome: Change in pre-post self-reported depressions scores

Exploratory Outcomes:

- Change in pre-post self-reported measures of confidence, self-compassion, sleep, resilience and well-being
- Change in Pre-Follow-up of self-reported measures of stress, depression, confidence, self-compassion, sleep, resilience, well-being

Aim 2: Describe the MBDC program based on participation, instructor and program satisfaction using a post-program survey

[figure not shown]
Approach

a. *Study design*

We are conducting a prospective pre-post observational study with members of the Mindfulness-Based Dementia Care (MBDC) program.

The MBDC program is an 8-week program designed for family caregivers for those living with dementia. The program is offered typically twice in a year at the HealthPartners Neuroscience center (program brochure attached) and other presence care project sites. Additional sites currently include the University of Michigan, the Ray Dolby Brain Health Center in San Francisco, and through a community offering in Grand Marais, MN. Participants attend a 1-hour orientation session, 2-hour classes each week for 7 weeks,

at-home practice between classes, and a 6-hour retreat. Some of the focuses of the weekly lessons include stress reduction, awareness of breath, grief contemplation, self-compassion, communication, responding to challenges, and mindfulness in everyday life. At the beginning and end of each weekly class, participants are evaluated based on their stress levels during the week prior and immediately after the class. At the end of the 8-week session, participants fill out a survey that includes a program evaluation, an instructor rating, and a self-evaluation of how well they will incorporate what they have learned from the course into their every-day life. Through surveys, the participant's mindfulness and well-being is also evaluated before, immediately after, and 3 months following the 8-week session. The following chart illustrates the timeline for this program, and the table indicates the study measures and at what point on the timeline they are evaluated.

The Program

Mindfulness-Based Dementia Care (MBDC) is an eight-week, group-based program designed for people who care for cognitively impaired individuals.

While not all stress is inherently bad, there are unique stressors experienced in the dementia care exchange that can become mentally, physically, and emotionally overwhelming. A mindfulness practice specifically geared to the care exchange offers invaluable resources and coping practices for responding to these stressors. The Mindfulness-Based Dementia Care program offers a way to establish a practice of mindfulness that is integrated with the day-to-day realities of caring for a loved one with dementia. Such a practice, especially if sustained over time, can help improve the quality of life for both the care partner and the person living with dementia.

MBDC groups typically consist of five to twelve participants. The program consists of seven two-hour sessions and one six-hour Day of Mindfulness. The sessions include formal meditations and informal mindfulness practices, role play, and lectures on dementia-related topics. Participants receive a workbook with literature related to the session topics and journaling prompts. The program also involves practice between classes.

Teaching and practices include formal meditation practices, as well as interventions borrowed from therapeutic modalities, such as Cognitive Behavioral Therapy, and Acceptance and Commitment Therapy. The goal is to reward participants with a transformative experience that may help sustain their wellbeing over the care journey. Though MBDC is not a therapy program, *per se*, it is quite therapeutic. It is also not a support group, but participants share that they feel very supported by the process, the intimacy of the program, and the new network of fellow dementia caregivers.

b. Population

i. *Inclusion/Exclusion Criteria*

Inclusion criteria:

- Must be ages \geq 18 years
- Must be able to read and understand English
- Participant of the MBDC Program at any site

ii. Sample size

The MBDC program at a time has only 12-15 participants. We hope to enroll at multiple offerings of the MBDC program. For the study, we plan to contact \sim 60 participants, and enroll \sim 50 in the study. Plan is to enroll through 5 sessions. Depending on the recruitment we may extend beyond the 5 sessions up to a maximum of 7 consecutive sessions. With multiple sites, we will be able to reach this number more quickly and prepare for a grant application to study the MBDC class as an intervention and include a control group.

c. Intervention, treatment

N/A. This is a prospective observational study of the MBDC program.

d. *Outcomes/endpoint and other variable definitions, and instruments used*

Please see all the surveys and the variables spreadsheet attached. The measures/instruments are defined below.

Primary Outcome: The Perceived Stress Scale (PSS): The Perceived Stress Scale is a widely used measure for stress perception. It measures how often and to what degree situations are characterized as stressful. This measure has been used to evaluate stress associated with chronic disease ⁹.

Secondary Outcome: Center for Epidemiologic Studies Depression Scale (CES-D): The Center for Epidemiologic Studies Depression Scale measures self-reported symptoms associated with depression. It has been validated for dementia and multiple other diagnoses, and it is sensitive to differences between caregivers and non-caregivers ¹⁰.

Exploratory Outcomes:

Self-Compassion: To evaluate self-compassion, participants indicated how often they acted in the manner stated in each of the items on a scale of 1 (almost never) to 5 (almost always). The survey evaluates self-kindness versus self-judgement, common humanity versus isolation, and mindfulness versus over-identification ¹¹.

Zarit Burden Inventory: The Zarit Burden Inventory is an interview that evaluates caregiver burden through a self-report measure. The survey scores are positively correlated with behavior problems in older adults and depression scores of caregivers ¹².

The Resilience Scale: The Resilience Scale has been used with people of different ages, education, and socioeconomic backgrounds. It evaluates the individual's stress, anxiety, forgiveness, and health-promoting activities ¹³.

Pittsburgh Sleep Quality Index (PSQI): This is a validated self-report questionnaire that evaluates sleep quality over a 1-month time interval ¹⁵. The measure takes about 5 min to complete.

Five Facet Mindfulness Questionnaire (FFMQ) Mindfulness: This scale evaluates five components, which includes observing, describing, acting with awareness, non-judging of inner experience, and non-reactivity to inner experience. This measure was developed by Ruth Baer at the University of Kentucky ¹⁶.

Likert Scale Stress Rating: Attitudes are measured by asking people to respond to a series of statements, indicating the extent to which they agree with them.

Confidence Survey: A set of questionnaires developed by University of Michigan to understand the confidence of caregiver in their ability to respond to caregiver needs and access to resources (questionnaire # 1, survey).

MBDC Program Evaluation Survey:

Program Evaluation: This survey demonstrates how the participant evaluates the quality and usefulness of the program.

Instructor Rating: The participant evaluates the instructor's ability to give clear expectations, knowledge of the subject matter, and attitude.

Participation in Practice: The participant reports the level of effort that they invested in formal meditation between classes.

e. Statistical analysis plan

Aim 1:

We will describe the patient characteristics using means and standard deviations (for continuous variables) and frequencies (for binary and categorical variables). Mean and standard deviations of scores for each of these validated scales will be calculated.

1. Pre-Post
2. Pre-Follow up

The mean and standard deviation of pre-post and pre-follow-up change in scores within participants will also be calculated. The 3 scores (pre, post and follow up) for each of the scales will be plotted on a histogram and we will describe any trends that we might see over time.

As the primary analysis, we will do paired t-test for change in scores of the PSS. As an exploratory analysis we will do a linear regression model with age and number of classes as covariates.

Aim 2:

We will describe the post-survey measures (evaluation of the program) using means and standard deviations (for continuous variables) and frequencies (for binary and categorical variables) and report qualitatively the themes of the open ended questions.

f. Power analysis or statement of precision

With a sample size of 50, the primary analysis is powered at 80% to detect a mean paired different of -1.8 with an estimated standard deviation of differences of 4.5, based on previous data from mindfulness program. This change is clinically meaningful and seems reasonable given previous research in this area.

g. Strengths and limitations

Strength: Pragmatic way of assessing the mindfulness program

Limitations:

1. Lack of control group in the study.
2. Limited sample size.
3. Observational study.
4. Multiple confounders

Risks and Benefits

There are almost no risks associated with being in this study. The standardized testing may make you uncomfortable because some parts may be too easy and you may feel self-conscious, while some parts of it may be difficult or tiring. The health history survey probes for personal health history information that may be sensitive information.

By being in this study you may or may not receive any direct benefit. You may feel better and more connected with the community.

Data Confidentiality and Privacy

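### The primary paired t-test on PSS drops everyone without both scores, and the plan gives no missing-data rule; if post-survey non-return is related to stress, the estimate for those enrolled can be biased

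*Combined protocol and SAP*

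**What the plan says.** The Study aims give the primary endpoint as "Primary Outcome: Change in pre-post stress scores". Section e (Statistical analysis plan, Aim 1) gives its only primary analysis: "As the primary analysis, we will do paired t-test for change in scores of the PSS". Section a (Study design) places the surveys at three times: "evaluated before, immediately after, and 3 months following the 8-week session".

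Section f (Power analysis) states: "With a sample size of 50, the primary analysis is powered at 80% to detect a mean paired different of -1.8", with an SD of differences of 4.5. Section b.ii (Sample size) uses the same number, about 50, for enrolment, from about 60 people contacted. It also allows more sessions: "Depending on the recruitment we may extend beyond the 5 sessions up to a maximum of 7 consecutive sessions".

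One other model is named: "As an exploratory analysis we will do a linear regression model with age and number of classes as covariates". It includes no stated way to handle a missing post score. No section gives an analysis set, an expected return rate, a missing-data method or a sensitivity analysis. The four limitations in section g do not mention unreturned surveys.

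**The concern.** A paired t-test needs two scores per person. Dementia caregivers are asked to complete several scales before the program, at its end and 3 months later, and the plan gives no reason to expect that every post survey will come back. A person who returns the pre survey but not the post survey contributes nothing to the primary estimate, even though the pre score, and perhaps a 3-month score, is in hand. The relevant event is survey non-return: someone who stops attending but returns the post survey stays in.

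The results are to go into a grant submission for a controlled study. If returning the survey is related to baseline stress or to how stress changed, the mean change among returners is not the mean change among those enrolled, and the plan has nothing that would show or reduce the difference.

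**Working it through.** **1. The plan's own power figure.** Inputs from section f: n = 50, mean difference -1.8, SD of differences 4.5. Alpha is not stated; two-sided 0.05 is assumed. The standardised effect is 1.8/4.5 = 0.4 and the noncentrality is 0.4 × √50 = 2.83. The noncentral t gives 79.2% power, and the normal approximation gives 80.7%. The stated 80% is reproduced, for 50 complete pairs.

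**2. Power with fewer pairs (50 enrolled, loss rate assumed).**

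| Assumed loss | Pairs | Exact power |
|---|---|---|
| 0% | 50 | 79.2% |
| 10% | 45 | 74.7% |
| 20% | 40 | 69.4% |

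**3. Bias when loss depends on baseline PSS.** The documents give no loss rate, mechanism, PSS standard deviation or pre-post correlation, so all of these are assumptions: 20% loss, log-odds of loss ±1 per SD of baseline PSS, equal pre and post SDs, and correlation ρ of 0.6 to 0.8. The SD of change (4.5) and the change (-1.8) are from section f.

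- With equal SDs, the SD of PSS is 4.5/√(2(1-ρ)): 5.03 at ρ = 0.6 and 7.12 at ρ = 0.8.
- The slope of change on baseline is ρ - 1. Per SD of baseline, change therefore differs by -0.4 × 5.03 = -2.01 at ρ = 0.6 and by -0.2 × 7.12 = -1.42 at ρ = 0.8.
- Integrating the logistic loss over a normal baseline, the returners' mean baseline is shifted by 0.173 SD.
- Error: 2.01 × 0.173 = 0.35 at ρ = 0.6, and 1.42 × 0.173 = 0.25 at ρ = 0.8.
- Paired mean: -1.45 to -1.55 if high-stress people are lost, -2.05 to -2.15 if low-stress people are lost. Simulated trials of n = 50 gave -1.44 to -1.57 and -2.02 to -2.15.
- With 40 pairs, SE = 4.5/√40 = 0.71, so the error is at most 0.35/0.71, about half an SE.

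**4. Weaker settings.** With log-odds ±0.5 at 20% loss, the simulated paired mean is -1.60 to -1.66 or -1.93 to -1.99, with 95% CI coverage of 94-95%. At 10% loss and log-odds 1, coverage is also 94-95%.

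**5. Dependence on the equal-SD assumption.** If the post SD is k times the pre SD, the slope becomes ρk - 1. At ρ = 0.8 and k = 1.25 it is zero, so there is no bias. At k = 1.43 it is +0.144 and the direction reverses: -1.93 when high-stress people are lost, -1.67 when low-stress people are.

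**6. What a repeated-measures model recovers.** These are simulations of 4,000 trials with n = 50, assuming that 80% of post returners and 25% of post non-returners give a 3-month PSS.

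| 20% loss | Paired mean | Coverage | Mixed-model mean | Coverage |
|---|---|---|---|---|
| Baseline-related, log-odds 1 | -1.44 to -1.57 or -2.02 to -2.15 | 92-94% | -1.77 to -1.81 | 94-95% |
| Related to lack of benefit, log-odds 1 per SD of change | -2.59 to -2.61 | 79-80% | -2.44 to -2.48 | 82-84% |

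Under random loss, root mean squared error is 0.70-0.73 (paired) and 0.69-0.72 (mixed). With complete data, the two give the same estimate, SE and 49 degrees of freedom.

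**7. Reading the lack-of-benefit row.** If returners average -2.6 and everyone averages -1.8, non-returners average (-1.8 + 0.8 × 2.6)/0.2 = +1.4. That scenario requires non-returners to worsen materially, so it is an extreme case.

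**The case against.** The strongest reply is that no loss rate is documented, so the bias is hypothetical. In the baseline-related case, moreover, the model improves root mean squared error only from 0.74-0.79 to 0.71-0.72. Both points are correct, and they limit the size of the concern. They do not remove it: the model uses scores already planned, costs nothing when all surveys return, and replaces a method that discards those scores.

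Several stronger readings are tempting, and the documents do not support them.

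- A reader might infer that the plan cannot use non-returners at all. That is true only of the primary test. Section e also summarises scores on each scale and pre-to-follow-up change, and says "we will describe any trends that we might see over time"; people without a post survey can enter some of these.
- A reader might infer that the primary result will overstate, or understate, the benefit. Step 5 shows that the direction depends on variances the documents do not give, and under random loss there is no bias.
- A reader might infer that attendance could repair the estimate. The documents do not show that class counts exist for non-returners: Aim 2 describes participation through a post-program survey. Section a says "At the beginning and end of each weekly class, participants are evaluated based on their stress levels", but not that those ratings are linked to study records. The attached surveys and variables spreadsheet are not in the text.
- A reader might infer that 50 pairs are unattainable. At 20% loss, 50/0.8 = 62.5, so 63 must be enrolled, against about 60 contacted. But seven sessions of 12-15 give 84-105 people, or 70-87 enrolled at 50 per 60 contacted. On the group size of 5-12 given in the program description, the total is only 35-84 people. So 63 is not shown to be out of reach. The extension is tied to recruitment; it could restore pairs but would not remove selection.

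**Conclusion.** The concern holds in limited form. The primary analysis is restricted to complete pairs, and nothing in the plan says how people without a post PSS are handled or how many are expected. With non-return unrelated to stress, the consequence is lost precision: 69.4% power at 40 pairs against 79.2% at 50. With non-return related to baseline PSS, the illustrated error is about 0.25 to 0.35 points on a change of -1.8. That rests on 20% loss, log-odds 1 per SD, equal SDs and a correlation of 0.6-0.8. It is small under milder assumptions and vanishes or reverses if the post SD is sufficiently larger than the pre SD.

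The 80% power figure is not an arithmetic error; it is correct for 50 complete pairs and silent about loss. This is a worthwhile, inexpensive improvement. It does not show that the planned result will be wrong.

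**What to change.** Amend section e as follows.

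- **Primary estimate:** post-minus-pre PSS change from a likelihood-based repeated-measures model, with time as a 3-level factor, unstructured within-person covariance, REML and Kenward-Roger degrees of freedom, on every enrolled participant with at least one PSS score. Keep the paired t-test on complete pairs as supportive.
- **Reporting:** n at each time, and baseline PSS and age compared between post-survey returners and non-returners. Add attendance if it is recorded for non-returners.
- **Sensitivity check:** set the non-returners' mean change to zero. The point estimate is the return fraction times the returner mean. At 20% loss, 0.8 × -2.6 = -2.08 in the lack-of-benefit case and 0.8 × -1.8 = -1.44 under random loss. Because it pulls toward zero when loss is random, present it as a check only.
- **Section f:** state the 80% power as conditional on 50 complete pairs, with 74.7% at 45 and 69.4% at 40, and state the alpha and sidedness.

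The cost is SAP wording and slightly more analysis work, with no new data. The model rests on an untestable missing-at-random assumption. If loss is driven by lack of benefit, it removes only 13-21% of the error in the simulated case, which is why the sensitivity check goes with it.

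### The exploratory regression has no site or offering term, so its number-of-classes coefficient may mix attendance with differences between offerings; reporting it with and without such a term is a cheap improvement

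*Combined protocol and SAP*

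**What the plan says.** Section e, Aim 1, makes a paired t-test on PSS change the primary analysis. It then adds, as exploratory, "we will do a linear regression model with age and number of classes as covariates". Those two covariates are the whole model. The outcome is not named; PSS change is inferred from the sentence before.

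Section a (Study design) describes a program "offered typically twice in a year at the HealthPartners Neuroscience center". It continues "Additional sites currently include the University of Michigan", a brain health center in San Francisco, "through a community offering in Grand Marais, MN". That makes four named sites, one of them a community setting.

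Section b makes eligible any "Participant of the MBDC Program at any site". Under Sample size it says "We hope to enroll at multiple offerings of the MBDC program" and "Plan is to enroll through 5 sessions", with a maximum of 7, for about 50 enrolled. I read sessions here as offerings of the eight-week program.

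No site, offering or instructor term, random effect, clustered standard error or by-site summary is planned. The limitations in section g mention confounding only in general terms. An instructor rating is collected, but only to be described under Aim 2.

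**The concern.** Offerings can differ in instructor, setting and time of year. Those differences can move both how many classes people attend and how much their PSS score changes. A pooled least-squares slope is a weighted average of the slope among caregivers in the same offering and the slope across offering means. The second part rests on only 5 to 7 means. If those means line up, the number-of-classes coefficient can be non-zero when attendance has no relation to change within any offering.

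Number of classes is the only covariate in the model that resembles an exposure, so a reader could take its coefficient as a dose-response. The Summary says the results will go into a later grant submission, and that is where a misread slope would matter. Nothing confirmatory in this study depends on it.

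**Working it through.** **The plan's own figure.** Section f gives 80% power for N = 50, mean difference -1.8 and SD of differences 4.5. With two-sided alpha 0.05 (assumed; not stated), the normal approximation is Phi(1.8/4.5 × √50 − 1.96) = 80.7%. The noncentral t with 49 df gives 79.2%. The figure reproduces and is not in dispute. The documents give no target for the exploratory model.

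**Inputs.**
- From the documents: N = 50; 5 to 7 offerings, so 50/5 = 10 to 50/7 ≈ 7 per offering; residual SD 4.5, borrowed from section f.
- Assumed: within-offering attendance SD (sw) 1.5 classes; between-offering SDs of 0.3 to 1.0 classes (sx) and 0.5 to 1.5 PSS points (sy); correlation ρ between offering means; true attendance effect zero.

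**Approximate expected slope without an offering term.** With K offerings of m people and age unrelated to either variable:

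slope ≈ m(K−1)·ρ·sx·sy / [m(K−1)·sx² + (Km−1)·sw²]

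For K = 5 and m = 10, m(K−1) = 40 and (Km−1)·sw² = 49 × 2.25 = 110.25.

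- SDs 0.3 and 0.5: 40 × 0.15ρ / (3.6 + 110.25) = 0.053ρ
- SDs 0.7 and 1.0: 40 × 0.70ρ / (19.6 + 110.25) = 0.216ρ
- SDs 1.0 and 1.5: 40 × 1.50ρ / (40 + 110.25) = 0.399ρ

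**Formula against simulation** (4000 data sets per setting, 5 offerings of 10; a range means that two or more independent runs were made):

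| SDs (classes, PSS) | ρ | Formula slope | Simulated slope | Rejection at nominal 5% |
|---|---|---|---|---|
| 0.3, 0.5 | -0.5 | -0.03 | -0.03 | 5.6% |
| 0.3, 0.5 | -1 | -0.05 | about -0.05 | not listed |
| 0.7, 1.0 | 0 | 0 | 0.003 | not listed |
| 0.7, 1.0 | +0.5 | +0.11 | +0.08 | not listed |
| 0.7, 1.0 | -0.5 | -0.11 | -0.09 to -0.10 | 6.1% to 6.8% |
| 0.7, 1.0 | -1 | -0.22 | -0.20 to -0.21 | 8.2% to 9.3% |
| 1.0, 1.5 | 0 | 0 | 0.001 | about 7% to 8% |
| 1.0, 1.5 | +0.5 | +0.20 | +0.18 | not listed |
| 1.0, 1.5 | -0.5 | -0.20 | -0.17 to -0.19 | 10.8% to 11.0% |
| 1.0, 1.5 | -1 | -0.40 | -0.37 to -0.38 | 19.8% to 20.6% |

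The formula runs slightly high because it takes a ratio of expectations. Seven offerings of 7 give slopes of -0.12 to -0.40 over the two larger SD settings at correlations -0.5 and -1. With offering indicators in the model, the slopes lie within 0.02 of zero and rejection is 4.4% to 5.5%.

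**A second set of assumptions** (total attendance SD 1.2, total SD of change 4.5) gives the same pattern:
- 10% of attendance variance and 5% of outcome variance between offerings, ρ = -0.8: slope -0.17 to -0.18, rejection 6% to 7%.
- 20% and 10%, ρ = -0.8: slope -0.34 to -0.37, rejection about 12%.
- 30% and 10%, ρ = -1, an extreme: slope -0.52 to -0.59, rejection about 20%.
- No between-offering variation in attendance, or variation unrelated to outcome: slope about 0.

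**Cost of the term.** Residual df are 50 − 3 = 47 as planned. They become 44 with three site indicators, 43 with five offerings and 41 with seven. In the runs with sw = 1.5, the model standard error rose by about 11% to 17% with five offerings (from about 0.39 to 0.41 up to 0.46) and by up to about 22% with seven. In the second set, the sampling SD of the slope rose by 2% to 13%.

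**Root mean squared error of the slope, without versus with the term:**
- SDs 0.7 and 1.0: 0.426 vs 0.458 at ρ = 0; 0.447 vs 0.463 at -0.5; 0.473 vs 0.462 at -1.
- SDs 1.0 and 1.5: 0.483 vs 0.466 at -0.5.

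**The case against.** The best defence is that this is a small exploratory model. Number of classes is called a covariate, no dose-response hypothesis is stated, and section g already admits an observational design, a limited sample and confounding. With mild clustering the planned model is also the more accurate one: its mean squared error is lower in two of the three settings with SDs 0.7 and 1.0. All of this stands. It argues against replacing the planned model, but not against showing both versions.

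Two further points stand. The excess rejection is not all bias: with the larger SDs, the test already rejects about 7% to 8% at zero correlation, which is unmodelled clustering. And offering indicators leave person-level confounding in place, such as less stressed caregivers attending more classes. With one or two offerings per site, they also cannot separate site from instructor.

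A reader might infer that the coefficient is certain to be biased, or that at least four sites are pooled. The documents support neither. Bias needs offering-level attendance and change to be correlated, and no data on either are given. Section a lists where the program currently runs; section b does not guarantee that every site contributes.

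A reader might also multiply the slope by seven classes and set the result against the -1.8 target. That compares an extrapolated contrast between attending none and attending all with a mean pre-post change, so it is no measure of importance.

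**Conclusion.** A minor point that holds conditionally. As specified, the slope combines within-offering and between-offering association, and the plan gives no means of telling them apart. Whether this matters depends on a correlation the documents do not report. Over the main assumed range, the average spurious slope runs from about 0 to about -0.40 PSS points per class, or the same with a positive sign, which could hide a benefit. At most that is about one standard error of the planned coefficient. Rejection runs from about 5% to 20%, including the clustering component. These figures rest on assumed between-offering SDs, an assumed attendance SD and PSS change as the outcome. The primary paired t-test has no attendance term, so this point does not touch it or its power.

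**What to change.** Add a sentence to section e, Aim 1: the exploratory regression of PSS change on age and number of classes will be reported as planned and again with offering as a fixed effect (site, if offerings are too small), and mean PSS change by site will be listed beside the pooled value. The adjusted coefficient then compares caregivers taught in the same offering, and a gap between the two versions shows how far the pooled one depends on differences between offerings.

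The cost is 3 to 6 degrees of freedom and a coefficient standard error roughly 11% to 22% larger in the adjusted version. With little clustering the unadjusted slope can be the more precise one, which is why both are reported. Site and offering must be recorded for each participant. That should follow from enrolment, but the variables spreadsheet attached to the protocol is not available here, so it should be checked. The report should also say that the offering term does not remove person-level confounding or separate site from instructor.

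### The 80% power in section f holds for 50 complete pre-post PSS pairs, but the plan enrols about 50 caregivers and allows for no missing post-program score

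*Combined protocol and SAP*

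**What the plan says.** All references are to the combined protocol and SAP.

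- **Study aims, Aim 1:** "Primary Outcome: Change in pre-post stress scores".
- **Section a (Study design):** surveys are "evaluated before, immediately after, and 3 months following the 8-week session". The primary outcome uses the first two of these time points.
- **Section e (Statistical analysis plan), Aim 1:** "As the primary analysis, we will do paired t-test for change in scores of the PSS".
- **Section f (Power analysis):** "With a sample size of 50, the primary analysis is powered at 80% to detect a mean paired different of -1.8". The paired differences are taken to have an SD of 4.5. Alpha and sidedness are not given, and the section does not say whether the 50 are enrolled caregivers or complete pairs.
- **Section b.ii (Sample size):** about 60 people are to be contacted, and about "50 in the study. Plan is to enroll through 5 sessions". It adds: "Depending on the recruitment we may extend beyond the 5 sessions up to a maximum of 7 consecutive sessions".
- **Section g (Strengths and limitations):** a limited sample size is listed, without a figure.

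The text gives no expected rate of missing post-program PSS, no inflation of the enrolment target, and no method for missing scores in the primary analysis.

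**The concern.** A paired t-test on the pre-post change uses only caregivers who have both scores, so the sample size that determines its power is the number of complete pairs. Section f uses 50 for that number and section b.ii uses about 50 for the number enrolled. The two agree only if every enrolled caregiver returns a PSS at the end of an eight-week program.

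Neither provision in section b.ii closes the gap. The step from about 60 to about 50 is loss between contact and enrolment, before anyone is in the study. The extension from 5 to 7 sessions depends on recruitment, so once about 50 are enrolled nothing in the text triggers it, however many post scores are missing.

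Power is the only operating characteristic the plan states, and the results are meant to support a grant submission for a larger controlled study. At stake is whether a reader of section f learns what 50 enrolled caregivers can detect.

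**Working it through.** **Inputs.** Mean paired difference 1.8 in absolute value, standard deviation of differences 4.5, sample size 50 and power 80% (section f); paired t-test (section e); about 60 contacted, about 50 enrolled, 5 sessions extendable to 7 (section b.ii). Assumed, because the documents do not give them: alpha 0.05 two-sided, and losses of 5%, 10% and 20%.

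**Step 1: reproduce the stated power.** The standardised effect is d = 1.8/4.5 = 0.40.

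- Normal approximation: power = Φ(d√n − 1.960) = Φ(0.40 × √50 − 1.960) = Φ(2.828 − 1.960) = 80.7%.
- Non-central t with n − 1 = 49 degrees of freedom, non-centrality 0.40 × √50 = 2.828 and critical value 2.010: power = 79.2%.

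Both agree with 80% to rounding. By non-central t, 51 pairs give 79.99% and 52 give 80.8%. One-sided 0.05 at 50 pairs gives 87.4%, which does not match, so two-sided 0.05 is the implied setting.

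**Step 2: power when some of the 50 enrolled have no post PSS.** Pairs = 50 × (1 − loss), rounded down. Power is by non-central t with d = 0.40 and two-sided 0.05. The last column is the difference detectable with 80% power at a standard deviation of 4.5.

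| Assumed loss | Complete pairs | Power | Detectable difference |
|---|---|---|---|
| 0% | 50 | 79.2% | 1.82 |
| 5% | 47 | 76.6% | 1.88 |
| 10% | 45 | 74.7% | 1.92 |
| 20% | 40 | 69.4% | 2.04 |

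The cost relative to no loss is 79.2 − 76.6 = 2.6 points at 5%, 79.2 − 74.7 = 4.5 points at 10%, and 79.2 − 69.4 = 9.8 points at 20%.

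**Step 3: enrolment that would keep 50 pairs.** Enrolment = 50/(1 − loss), rounded up: 50/0.95 = 52.6, so 53; 50/0.90 = 55.6, so 56; 50/0.80 = 62.5, so 63.

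**Step 4: what the permitted extension could yield.** The plan's own rate is 60 contacts over 5 sessions, or 12 per session, with 50/60 of those contacted enrolling. Seven sessions give 7 × 12 = 84 contacts and 84 × 50/60 = 70 enrolled. At 20% loss that is 70 × 0.80 = 56 pairs.

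**The case against.** **Section f is correct as worded.** It is a conditional statement about a sample size of 50, and it reproduces. This stands. The difficulty appears only when it is read beside the enrolment target in section b.ii.

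**No loss is documented, and the primary score is taken at the end of the program, not at the 3-month follow-up.** This also stands. Every reduced power above rests on an assumed rate, and at 5% the cost is under 3 points. What does not depend on a rate is that the enrolment target leaves no room for any loss.

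**The effect is within the uncertainty of the inputs.** Losing 10% has about the same effect as a standard deviation of 4.75 in place of 4.5 at 50 pairs (74.8%). Conversely, 45 pairs with a standard deviation of 4.2 give 80.3%. Enrolment is itself approximate. This limits the weight of the point. But uncertainty in the standard deviation can go either way, whereas missing scores can only reduce the number of pairs.

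**The extension is large enough.** At the plan's own contact rate it is (step 4). It is a possible remedy, however, not a stated allowance, because it is tied to recruitment.

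**The limitation is disclosed.** Section g names the sample size as limited but does not say that the 80% requires complete data.

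**Stronger readings that a reader might infer.** The normal-approximation formula gives ((1.960 + 0.842)/0.40)² = 49.06, which rounds up to 50, so one might conclude that 50 was calculated as a bare minimum and attrition then forgotten. The documents do not say how 50 was reached; power computed for a feasible number reads equally well. One might also conclude that the study will be underpowered. That needs a loss rate, which the documents do not give.

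**Conclusion.** The point holds as a minor one. The stated 80% is correct to rounding for 50 complete pre-post PSS pairs, and the planned enrolment of about 50 delivers it only with zero loss. Under assumed losses of 5% to 20%, power is about 77% to 69%, and 80% power applies to differences of about 1.9 to 2.0 in place of 1.8. These figures rest on two-sided alpha 0.05 (implied, not stated), the plan's standard deviation of 4.5, exactly 50 enrolled, and loss rates chosen for illustration.

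The arithmetic in section f is not in error. A smaller number of pairs does not in itself invalidate the paired t-test. It makes the result less precise than the plan states, in a study that already acknowledges having no control group and a limited sample.

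**What to change.** Restate section f in complete pairs, name alpha, and show an assumed loss range, for example:

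> 50 complete pre-post PSS pairs give about 80% power (two-sided alpha 0.05) for -1.8 with SD 4.5. With 50 enrolled and an assumed 5-20% lacking a post PSS, 47-40 pairs give about 77-69% power, or 80% power for about -1.9 to -2.0.

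If the study team has its own estimate of loss, that should replace the 5-20%. This is wording only: analysis, enrolment target and recruitment are unchanged. The cost is that the stated power becomes slightly less favourable. The rewording adds no pairs; it makes the claim match the enrolment.

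Optionally, judge the already permitted extension to 7 sessions on complete pairs instead of recruitment. That is an operational change. It would mean enrolling about 56 at 10% loss or 63 at 20% loss to keep 50 pairs, both within the 70 that seven sessions would yield at the plan's own contact rate and uptake.
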